1.0 Project Summary/Abstract

[figure not shown]
Background: Pregnancies conceived within 18 months of a prior delivery (termed short inter-pregnancy interval [IPI]) place mothers and infants at high risk for poor health outcomes including pre-eclampsia, anemia, and preterm birth.^{1,2,3-7} Despite these negative health consequences, nearly one third of women experience a short IPI, highlighting a significant public health problem in the U.S.⁹ A critical approach to preventing short IPIs is to provide postpartum (PP) women with timely access to contraception. The current standard clinical practice is to have women return six weeks after delivery for a postpartum visit, at which time contraceptive needs are addressed. However, many women resume sexual activity prior to six weeks PP, and many women, particularly low-income minority women, do not present for this visit. Low rates of postpartum contraception uptake leave women vulnerable to an unplanned pregnancy and significant negative health consequences. Thus, there is an urgent need for alternative approaches to increase timely access to PP contraception to improve outcomes for women and children.

Objectives: The study aims to: (1) develop a comprehensive implementation plan to link PP contraception and newborn care through co-scheduling visits in community health centers (CHC) and (2) use an effectiveness- implementation hybrid design to evaluate this novel system-level approach to linking maternal and newborn care at CHCs served by our partner organization, AllianceChicago. Lastly, we aim to: (3) assess implementation of linked PP contraception and newborn care and report on key barriers and facilitators related to successful implementation of the intervention.

Methods: Using a novel approach, we will test a patient-oriented alternative delivery system for PP contraception that will fill a gap in our current system resulting in improved contraceptive access for women. We will use a cluster randomized cross-sectional stepped wedge design to test the novel linked contraception and WBV model's impact on increasing PP contraception uptake in urban and rural CHCs, compared to usual care.

Outcomes: It is expected that the intervention will increase the proportion of women using contraception and 2 and 6 months postpartum. Increasing access to timely contraception is a promising strategy to help women plan their families and, in turn, reduce the poor health sequela associated with short IPI pregnancies. The long-term impact of this study is to reduce negative health outcomes among PP women and infants by increasing access to patient-oriented PP contraceptive care. Findings may provide evidence supporting a paradigm shift for linked PP care and identify important insights to facilitate successful implementation of this model of care in CHCs across the nation.

Figure 1: Hypothesis—Linking contraception with newborn care will decrease unintended pregnancies and improve maternal and child health outcomes

2.0 Background/Scientific Rationale

Pregnancies conceived within 18 months of a prior delivery (termed short inter-pregnancy interval) place mothers and infants at high risk for poor health outcomes including pre-eclampsia, anemia, and preterm birth.^{1,2,3-7} Additionally, among women who experience a short IPI, 74.4% report the pregnancy was unintended.⁸ Despite these negative health consequences, nearly one third of women experience a short inter-pregnancy interval, highlighting a significant public health problem in the U.S.⁹

Consistent contraception use is the most effective way to prevent unintended pregnancies.¹⁰ Unfortunately, rates of postpartum (PP) contraception use remain low leading to high rates of unintended pregnancy and short IPIs.¹¹ Few women receive contraception prior to the standard six-week PP visit, and many do not receive contraception until *after* six-weeks PP.¹¹ Among a group of low-income publicly-insured women in California (N= 117,664) followed for 18 months PP, only 42% received contraception at *any* time between delivery and 90 days PP, and as few as 13% received contraception at their *first* PP visit.¹¹ Additionally, over a third (36%) of these women had a short IPI pregnancy.¹¹ Low rates of PP contraception uptake leave women vulnerable to an unplanned pregnancy and significant negative health consequences. Reducing the national level of unintended pregnancies is important for women and families, and is an important reproductive health goal identified by the United States Department of Health and Human Services (DHHS).¹² Increasing access to timely PP contraception is a promising strategy to help women plan their families and, in turn, reduce the poor health sequela associated with short IPI.

Low-income women are most at-risk for unintended pregnancies and least likely to receive timely contraception. More than 19 million U.S. women need publicly supported contraceptive services, and of those in need, 5.8 million (30%) are uninsured.¹⁰ While overall rates of unintended pregnancies have been decreasing since the 1980s, the decrease has been primarily among higher-income women. A recent study reported significant disparities in unintended pregnancy rates by income, with low- income women significantly more likely to experience an unintended pregnancy underscoring the importance of testing approaches to meet these women's contraceptive needs.¹³

Reproductive health services are limited in many rural areas, contributing to less access to health care and poorer maternal and infant health outcomes.¹⁴ A telephone survey of reproductive age women in Central Pennsylvania in 2004-2005 found rurality impacted contraceptive counseling, with women in rural areas significantly less likely than urban women to receive counseling related to birth control.¹⁵ Sexually active women living in rural areas are also less likely to receive reproductive health services compared to women in urban areas, with approximately 16.9% and 83.1% receiving family planning services in the past 12 months, respectively.^{14,16} Given this unmet need for reproductive health services in rural areas, efforts should also focus on strategies to increase access to and provision of contraception for rural women.

Community Health Centers (CHCs) serve as a safety net for low income underserved urban and rural residents.¹⁷ Research has shown that 83% of individuals who receive care at CHCs have a form of public insurance or no insurance, while only 39% of patients who seek care at private physician offices are uninsured or have public forms of insurance.¹⁸ Overall, CHCs serve an estimated 24% of all low-income women of childbearing age in the U.S.¹⁹ Despite the varying scope and delivery of family planning services across CHCs, virtually all CHCs have reported that they provide at least one contraceptive method (99.8%) at one or more clinical sites.¹⁹ Most CHCs are adequately equipped to provide comprehensive contraception counseling and provision of a broad range of contraceptive methods to medically underserved communities. Therefore, CHCs serve as an ideal setting for a program intended to reach the women most in need of improved contraception services in the PP period.

The current standard of care is to address women's PP contraceptive needs at the six-week PP visit. However, this model of care is ineffective for many reasons, particularly for low-income women. First, many women resume sexual intercourse before six-weeks PP and prior to initiation of contraception.^{20,21} Second, many women do not attend the six-week PP visit.²² Prior analyses of Illinois Medicaid data by our team, and an analysis of California Medi-Cal data, found PP visit rates to be 56% and 49.4% (respectively).^{22,23} In addition, health disparities exist resulting in African-American women and women living in high poverty communities experiencing the lowest rates of PP care.²² Third, few women who return for PP care receive contraception at this time due to a provider barrier (i.e., inadequate time to address contraception at the visit, less skilled providers with lack of knowledge about medically appropriate PP contraception or requiring return visit for placement of long-acting methods).¹¹ Fourth, the timing of the six-week PP visit is based on tradition rather than evidence supporting improved patient outcomes.^{24,25} Finally, efforts to date such as antenatal discussion of the importance of the PP visit, use of discharge planners to encourage PP follow-up, and email and text reminders have had limited impact on increasing attendance at PP visits or contraception use.^{26,27} This has led to testing alternative strategies to improve uptake of PP contraception, such as providing contraception prior to hospital discharge after delivery.^{28,29} Unfortunately, efforts to increase immediate PP contraception provision have also faced significant implementation challenges due to lack of knowledge among providers of appropriate immediate PP contraception options, financial concerns regarding billing and reimbursement, and competing clinical and administrative priorities.³⁰ **Thus, there is an urgent need for new approaches to improve timely access to contraception for PP women.**

A highly promising opportunity to reach PP women is to counsel and provide contraception at the newborn care visit. Nearly all mothers routinely bring their infants in for newborn care during the first six months of life.^{31,32} In 2009-2010, 93.2% of women reported that their infant had a well-baby visit (WBV) within one week of birth, and in 2011-2012, 90.9% of U.S. infants attended WBV visits during the first year of life.³² The American Academy of Pediatrics recommends normal infants have WBVs at 3-5 days post hospital discharge and by one month of age (both of which are prior to the standard

PP visit) and four more visits before one year (i.e., two, four, six, and nine months).³² Hence, the newborn care visit is an opportunity to reach more women than are reached through the current standard PP visit model of care and there is precedent for linking maternal health care to infant care. Addressing maternal health needs during a pediatric visit is now standard practice for pediatricians with respect to screening for PP depression. Evidence supports findings that PP depression screening is reliable and feasible in the pediatric setting, which led to national systematic changes to include PP depression screening at the WBV.³³ Furthermore, research efforts are beginning to study the feasibility of management of PP depression within pediatric care.³⁴ Routine infant health care visits represent the most regular contact new mothers have with the health care system, making it an ideal venue for implementing timely PP contraception care.³⁵

This study will use a novel patient-oriented approach to link (co-schedule) PP contraception care with newborn WBV care (Figure 1). Though this model of co-scheduling care for mothers and newborns may appear intuitive, the current model of health care in the U.S. is *individual-patient* focused. Even in clinical environments where care is provided to both mothers and infants (i.e., family medicine clinic), the care is rarely coordinated. Continuity of care for families with the same primary care clinician or practice has been associated with improved outcomes, including increased use of preventive services, better adherence to clinician recommendations, and lower total costs, although this model of care has not been well studied in the context of maternal and child care delivery.³⁶ Our relatively small system-level change in scheduling practice linking maternal contraceptive care with newborn care could have a very large impact on women's receipt of care and contraception. In addition, by offering co-scheduled care to all PP women the model explicitly acknowledges the importance of PP care directly to new mothers. If successful, the model of care could be implemented broadly in a variety of health care settings. This project will contribute to national efforts to improve maternal health and decrease unintended pregnancies and short IPI pregnancies specifically addressing the *Healthy People 2020* goal to decrease unintended pregnancy by ten percent.^{12,37} **Finally, results from this project will take the next step in informing the science to improve care delivery strategies to provide comprehensive PP care for women.**

Based on our findings, **we hypothesize that providing PP women contraception care linked with newborn care through co-scheduling these visits will increase the number of women offered contraception prior to two and six months PP and reduce the number of short interval pregnancies.** We will use an effectiveness-implementation hybrid design guided by two implementation science frameworks (CFIR and RE- AIM) to evaluate this novel system-level approach linking maternal and newborn care at community health centers served by AllianceChicago, our partner organization. AllianceChicago focuses on improving clinical care for vulnerable populations, and has significant experience in community-based research.

The long-term impact of this study is to reduce negative health outcomes among PP women and infants by increasing access to patient-oriented PP contraceptive care.

Findings may provide evidence supporting a paradigm shift for linked PP care and identify important insights to facilitate successful implementation of this model of care in community health centers across the nation.

3.0 Objectives/Aims

Aim 1: Develop a comprehensive implementation plan to link PP contraception and newborn care through co-scheduling in community health centers. We will work with AllianceChicago to assess community health center fit and readiness. Guided by the *Consolidated Framework for Implementation Research (CFIR)*, we will interview administrators, staff, providers, and patients from each site with the goal of identifying factors that may facilitate or impede the development of an implementation plan for linked care.

All study activities for Aim 1 have been completed.

Aim 2: Implement linked PP contraception and newborn care in seven geographically diverse community health centers (six urban and one rural) and evaluate the effect on provision of PP contraception and rates of short-interval pregnancy. We will roll out the intervention across sites with a stepped-wedge, cluster-randomized design and use AllianceChicago's common electronic health record to evaluate effectiveness by comparing pre- and post-intervention outcomes including clinic-level provision of all methods of contraception at two and six months PP and clinic-level rates of short inter-pregnancy intervals.

Hypothesis: we hypothesize that providing PP women contraception care linked with newborn care through co-scheduling these visits will increase the number of women offered contraception prior to two and six months PP and reduce the number of short interval pregnancies.

All participating CHC's have been randomized for the intervention. All sites entered the control period April 1, 2021 and the first site will enter the intervention period August 1, 2021.

Aim 3: Assess implementation of linked PP contraception and newborn care and report on key barriers and facilitators related to successful implementation of the intervention. A mixed methods approach will be utilized to assess and document the implementation process using the *RE-AIM (Reach, Effectiveness, Adoption, Implementation, and Maintenance)* and CFIR frameworks.

4.0 Study Design Background

Implementation science methods can be used to test the impact of linking maternal care with infant care in CHCs and used to enhance the utility of findings. From a design standpoint, hybrid trials are increasingly being utilized in implementation research

to simultaneously assess the clinical and implementation outcomes resulting from the introduction of a clinical intervention in a new context.³⁸ Traditional trial designs that focus only on clinical patient outcomes often fail to capture complex details of the implementation of the intervention and what factors impact implementation across different settings.³⁹ As a result, the public health impact of clinical studies is too often not fully realized because evidence is lacking for how interventions can successfully be brought to scale or translated to other settings. **Hybrid trials can speed the pace of translation by generating evidence about both the clinical effectiveness of an intervention and factors influencing successful implementation in a given setting.**

Implementation science also provides relevant conceptual and measurement frameworks to guide a hybrid trial of clinical outcomes and implementation factors. For instance, the **Consolidated Framework for Implementation Research (CFIR)**, which has been used to guide the implementation and evaluation of numerous evidence-based health programs, synthesizes the concepts of several available models into five inter-related domains: intervention characteristics, outer setting, inner setting, characteristics of individuals involved, and the process of implementation, with several constructs in each domain.⁴⁰ CFIR accounts for the non-linear process of implementation and incorporates consideration of the adaptation that is required for different contexts, making it a useful framework for studying the implementation of linked maternal and infant care in CHCs. CFIR also describes several constructs particularly relevant to this intervention, a sample of which is provided in Table 1 (see approach).

The **Reach, Effectiveness, Adoption, Implementation, and Maintenance (RE-AIM) framework** is an evaluation and reporting scheme commonly used to examine the potential public health impact of an intervention.⁴¹ *Reach* represents the number and representativeness of patients who participate out of the eligible patient population. *Effectiveness* is the impact of the intervention on participant outcomes. *Adoption* is the number and representativeness of eligible staff/settings that agree to deliver the intervention out of all eligible staff/settings. *Implementation* is the fidelity to the intervention. *Maintenance* is the degree to which the intervention is sustained over time. RE-AIM provides a useful measurement framework for capturing both clinical and implementation outcomes within the same study. **Integrating CFIR and RE-AIM within a hybrid clinical effectiveness and implementation trial will generate the evidence needed to rapidly translate the findings from a clinical trial of linked care maternal and infant care to standard practice.**

5.0 Aim 1 Research Design, Methods, and Data Analysis

Aim 1 is to develop a comprehensive implementation plan to link PP contraception and newborn care through co-scheduling in community health centers. Our research team has demonstrated that, despite favorable patient attitudes towards linked care, delivery needs to consider physician, clinic and patient factors, which may influence implementation in the CHC setting. To that end and guided by CFIR, Aim 1 will assess clinic, staff and patient factors that may affect successful implementation of linked care.

A CFIR (Table 1) construct important for successful implementation within the inner setting (CHC-level) domain is readiness for implementation.⁴⁰ We partnered with AllianceChicago to engage the CHC sites identified as eligible and introduced the intervention to find out which sites are interested in participating in the study. We will recruited seven CHCs total (six urban and one rural) from AllianceChicago's network.

5.2 Aim 1a: Staff and Clinic Structure Assessment

Participating CHCs were asked to select 4-6 staff to participate with representation from administration, physicians providing pediatric or PP services, nurses and ancillary staff including schedulers. **Key informant interviews** were conducted with selected CHCs by Drs. [name] and [name] and their investigative team to identify features of the individual CHCs and the overall network that are potential barriers and facilitators to implementation of the intervention. Semi-structured interview guides were developed to ensure consistency of qualitative data collected while allowing for open-ended responses. Questions and prompts were developed to solicit information about the CFIR constructs, which will be closely reviewed by both PIs before conducting interviews (see Table 1 for a sample of relevant constructs).

Table 1: Consolidation Framework for Implementation Research Constructs for Linking Postpartum and Newborn Care	
Construct	Description
INTERVENTION CHARACTERISTICS	
Adaptability	The degree to which the intervention can be adapted or reinvented to meet patient and CHC needs. (SA1)
Complexity	Perceived difficulty of implementation. (SA1, SA3)
Relative Advantage	Postpartum women and CHC's perception of the advantage of implementing the intervention. (SA1)
OUTER SETTING	
Patient Needs & Resources	The extent to which postpartum women's needs and preferences are accurately known and prioritized by CHCs. (SA1)
INNER SETTING	
Readiness for Implementation	Tangible and immediate indicators of CHCs commitment to implement the intervention. (SA1)
CHARACTERISTICS OF INDIVIDUALS IN CHCs	
Personal Attributes	Traits of physicians and staff in CHCs. (SA1)
PROCESS	
Planning	Tasks for implementation are developed in advance, and the quality of the methods. (SA1)
Champions	CHC staff (clinical and administrative) who drive the implementation of the intervention. (SA1)
Executing	Carrying out or accomplishing the implementation according to plan. (SA 2, SA 3)
Reflecting & Evaluating	Quantitative and qualitative feedback from physicians and staff about the progress and quality of implementation. (SA3)

Adapted from the Damschroder et al. 2009

5.3 Aim 1b: Patient Assessment

PP women (<9 months PP) who are attending a WBV were asked for voluntary participation in an interview by phone. Interviews were conducted by Drs. [name] and [name] and their investigative team with 3 patients per site. **Key informant interviews** were conducted to identify women's preferences and needs regarding PP contraception as well as obtain feedback on the intervention. Semi-structured interview guides were developed by the PIs to ensure consistency of qualitative data collected while allowing for open-ended responses. Questions and prompts were developed to solicit information about the CFIR constructs relevant to patient experience (Table 1).

5.4 Data Analysis

All interviews were audio-recorded and transcribed. Qualitative data was coded according to CFIR constructs. Emerging themes were identified and categorized as adaptable components of the intervention (barriers or facilitators) then compared across the urban and rural sites. All interviews were reviewed carefully by both PIs to determine clinically relevant aspects particular to ensuring successful implementation development. Themes as well as data from the readiness for implementation instrument were used to develop an implementation plan for the adapted clinical intervention that includes strategies to address potential barriers.

All study activities for Aim 1a and 1b have been completed.

6.0 Aim 2 Research Design, Methods, and Data Analysis

Aim 2 is to implement linked PP contraception and newborn care in 7 CHCs and evaluate the effect on provision of PP contraception and rates of short-interval pregnancy. We hypothesize that a linked PP contraception care with newborn care model can be implemented successfully in urban and rural CHC settings. PP women offered contraceptive care linked with newborn care would be more likely to receive any form of contraception at two months PP and by six months PP. Additionally, we hypothesize that CHCs will have a lower rate of short IPIs among incoming prenatal patients after implementing the linked contraception care with newborn care model compared with their rate prior to implementation.

Using a novel approach, we will test a patient-oriented alternative delivery system for PP contraception that will fill a gap in our current system resulting in improved contraceptive access for women. We will use a cluster randomized cross-sectional stepped wedge design to test the novel linked contraception and WBV model's impact on increasing PP contraception uptake in urban and rural CHCs, compared to usual care. We will include the 7 CHCs (six urban, one rural) recruited through Aim 1 of this project.

During the intervention period, staff will capture women during the first WBV (typically 3-5 days after delivery) and offer to have the next visit co-scheduled for infant and contraception care. Current practice at all AllianceChicago CHCs is to ensure all newborn infants leave the clinic with the next visit already scheduled. Appointments are scheduled during the discharge process at the end of each visit. During the discharge process all women 0-6 months postpartum who are established patients will be identified by an electronic prompt in the infant's electronic medical record. The prompt will instruct staff to offer the mother a co-scheduled visit for newborn and contraceptive care at the time of the next newborn visit.

Those who agree will be co-scheduled and those who are not in need of care, or do not wish for co-scheduled care, can decline. Women will be excluded if they had a tubal ligation or a long acting reversible contraception planned immediately after delivery. Women will be offered this co-scheduling option at each WBV through six months PP. Repeat opportunities for co-scheduled care are important as women's needs and

preferences change over time. Prior to initiation of the scheduling change, the PIs with [name] and the site clinical champions, will conduct several training sessions of the clerical staff, support staff, and clinicians. Training for clinicians will emphasize appropriate medical knowledge about PP women's overall care needs including contraception needs. We will brief clinicians on the linked model of care. Training with staff will focus on the need for a linked model of care and logistical considerations.

A key element of the research infrastructure will be AllianceChicago's uniform electronic health record system (EHRS), which is distinguished by the integration of evidence-based practice recommendations into the end user interface to provide decision support at the point of care. AllianceChicago's information technology (IT) team will build custom templates to match PP women and their infant's records. They will create a study-specific field in the EHR during well-baby visits for infants 0-6 months to prompt and record the offering of a co-scheduled appointment for the mother during the discharge process. The prompt will be rolled-out consistently among all sites based on the step-wedge design (below).

We will conduct a cluster randomized, cross-sectional stepped wedge study to roll out the intervention across sites and assess the change in clinical and implementation outcomes from before to after the adapted intervention is introduced into clinics. The cluster, or unit of analysis, is the clinic (not individual), which is critical for a system-level intervention. In a stepped wedge study, the design is extended so that every cluster provides before and after observations and every cluster switches from the control (usual care) to the intervention condition (linked care) at regular intervals ("steps"), at different points in time. The order in which a cluster switches from control to intervention is randomized. The advantages of the stepped wedge design are that it provides a pragmatic and robust approach to testing the effectiveness of health service delivery interventions (53). The stepped wedge design is pragmatic because the intervention can be rolled out over time. Additionally, no individual patient consent is required for this system-level health service delivery intervention, and therefore outcomes may be obtained through routinely collected de-identified data from the common AllianceChicago EHR. It is a robust design because each cluster provides data under both the control and intervention condition and therefore may serve as its own control, improving the precision of the study. A limitation of the stepped wedge design is the confounding effect of time given that clusters switch over to the intervention at different times. To help control for the effect of time, 4 additional clusters will be randomized to either the control or the intervention for the entire study period, as in a traditional parallel cluster randomized trial.

One urban and one rural CHC site will be randomized to each step occurring at 3-month intervals. Each step includes a 3-month transition period when the individual clinics will prepare to implement linked care. The design is cross-sectional because outcomes are obtained from the subset of patients seen during each time period at each clinic rather than following individually recruited patients over time.

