6.1 Eligibility

Eligible participants include women presenting with their infants at one of the 7 chosen CHC sites for their first WBV (typically 3-5 days after delivery).

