6.1.1 Inclusion Criteria

- Women bringing infant for their first WBV at chosen CHC

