6.1.2 Exclusion Criteria

- PP tubal ligation
- Emergency hysterectomy due to life threatening bleeding during the delivery

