6.2 Outcome Variables

Primary outcome:

- **Receipt of all methods of contraception by two months PP.** Using de-identified patient-level EHRS data for eligible women at each clinic within each time interval, we will create a dichotomous variable for receiving any contraception by two months PP. We will work with AllianceChicago's IT team to restrict the data pull to eligible women who attended an infant 3-5 day WBV after the study period began.

Secondary outcome:

- **Receipt of all methods of contraception by six months PP.** This outcome will be calculated similar to the primary outcome with the exception of time-period.
- **Short IPI pregnancies.** During the baseline period (control condition) and 18 months after the introduction of the intervention in each CHC, we will use EHRS data to estimate the clinic-level rate of incoming prenatal patients presenting with a short IPI.

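### Does the LARC exclusion in section 6.0, absent from section 6.1.2, leave the primary-outcome denominator undefined?

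*Combined protocol and SAP*

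**What the plan says.** The protocol touches on who counts in three places.

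- **Section 6.0 (Aim 2 design).** After describing the offer of a co-scheduled visit in the intervention period, the text says "Women will be excluded if they had a tubal ligation or a long acting reversible contraception planned immediately after delivery". A little earlier, on the discharge process, it says "all women 0-6 months postpartum who are established patients will be identified by an electronic prompt".
- **Section 6.1 (Eligibility).** "Eligible participants include women presenting with their infants at one of the 7 chosen CHC sites for their first WBV". The inclusion criterion in 6.1.1 is "Women bringing infant for their first WBV at chosen CHC". The two exclusions in 6.1.2 are "PP tubal ligation" and "Emergency hysterectomy due to life threatening bleeding during the delivery". LARC is not listed.
- **Section 6.2 (Outcome Variables).** For the primary outcome, "we will create a dichotomous variable for receiving any contraception by two months PP", and the IT team will "restrict the data pull to eligible women who attended an infant 3-5 day WBV after the study period began".

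Section 6.5 anticipates a rise from 45% to 60% and does not say whether women with immediate LARC are counted in those rates. The RE-AIM table in section 7.1 also takes percentages of eligible women and gives no further definition.

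**The concern.** Neither exclusion text contains the other: section 6.0 omits hysterectomy and section 6.1.2 omits LARC. Section 6.2 does not say which one defines an eligible woman.

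LARC is not an ordinary exclusion here, because it is itself contraception. A woman with LARC placed at delivery, if it is recorded, has the primary outcome whatever the clinic does. Keeping or removing her therefore changes both numerator and denominator. Section 6.0 also speaks of LARC that is planned, whereas section 6.3 builds the data pull from ICD, CPT and HCPCS codes.

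If both readings were equally open, two analysts could report different control rates and different absolute effects from the same data. If the exclusion were applied only in the intervention period, which is where section 6.0 introduces it, the before-and-after comparison within clinics would be biased.

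**Working it through.** **Which reading the text supports.** Setting the sections side by side:

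1. Section 6.1 carries the heading Eligibility, with formal inclusion and exclusion lists. Section 6.2 follows at once and uses the word eligible. The nearest and only formal referent is 6.1.
2. The LARC sentence in 6.0 stands between one saying that women may decline co-scheduling and one saying that the offer is repeated at each WBV through six months. Its surroundings concern the offer.
3. The 6.0 sentence leaves out hysterectomy, so it does not look like a full statement of eligibility.
4. A plan for LARC is something staff can ask about at discharge. The documents do not say that such a plan, or LARC placed at the delivery hospital, reaches the health-centre record. That makes it an unlikely analysis filter. If the sentence governs only the offer, planned versus placed does not affect the primary outcome.
5. Section 6.2 draws eligible women at each clinic within each time interval. That describes one definition for all periods, and nothing in the documents applies the exclusion in one period only.

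The two side questions are answered in the same way. In 6.0, established patients are the women the prompt identifies, and 6.1 has no such criterion. Both 6.0 and 6.1 describe the first WBV as typically 3-5 days after delivery, so the visit named in 6.2 is the first WBV.

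**What the choice would cost.** There is no stated figure to reproduce: the plan gives no sample size, power or LARC share. The inputs are 45% and 60% from section 6.5 and an assumed share L of women with immediate LARC (5, 10, 15%). L is taken as equal in both periods and unaffected by the intervention.

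*(a) The rates include LARC users, who count as receiving contraception, and they are removed:* rate = (p − L)/(100 − L).

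| L | Control | Intervention | Difference |
|---|---|---|---|
| 5% | 40/95 = 42.1% | 55/95 = 57.9% | 15/0.95 = 15.8 |
| 10% | 35/90 = 38.9% | 50/90 = 55.6% | 15/0.90 = 16.7 |
| 15% | 30/85 = 35.3% | 45/85 = 52.9% | 15/0.85 = 17.6 |

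The control rate falls by 2.9, 6.1 or 9.7 points.

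*(b) The rates exclude LARC users, who are then added as receiving contraception:* rate = L + (1 − L/100)p.

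| L | Control | Intervention | Difference |
|---|---|---|---|
| 5% | 5 + 0.95 × 45 = 47.75% | 5 + 0.95 × 60 = 62.0% | 14.25 |
| 10% | 10 + 0.90 × 45 = 50.5% | 10 + 0.90 × 60 = 64.0% | 13.5 |
| 15% | 15 + 0.85 × 45 = 53.25% | 15 + 0.85 × 60 = 66.0% | 12.75 |

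*(c) As (a), but LARC placed at delivery is not recorded as receipt:* control 45/(100 − L) = 47.4, 50.0, 52.9%; intervention 60/(100 − L) = 63.2, 66.7, 70.6%. The differences are again 15.8, 16.7 and 17.6 points.

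**Null check.** If the intervention does nothing, both periods have the same p. Each formula then gives the same value twice, and the difference is 0.

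**Uneven use.** If recorded LARC users were dropped in the intervention period only, a null effect would appear as −2.9, −6.1 or −9.7 points. That is the damaging case, and the plan does not call for it.

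**The case for a change.** The best case for a change is that the LARC sentence says women will be excluded, not that they will not be offered a visit. It also pairs LARC with tubal ligation, which 6.1.2 treats as a study-level exclusion. A careful reader could therefore apply both lists. The outcome comes from a routine data pull, so the filter is the analysis population, and leaving it open would allow a choice after rates have been seen. One clarifying sentence would cost almost nothing.

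Much of this stands. The mismatch is genuine, section 6.2 has no cross-reference, and the reading through 6.1 remains an inference. The control rate could differ by several points between the two readings.

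The objection does not show that following section 6.1 gives a wrong answer, nor that a denominator without LARC users would be better. Removing them isolates the women whose outcome the offer could change. Keeping them describes the effect across the clinic's eligible postpartum population, which suits a system-level intervention and does not depend on identifying LARC from records that may not hold it. Either is defensible.

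**Conclusion.** No change to the plan is called for. The protocol has a wording mismatch on LARC between section 6.0 and section 6.1.2. An analyst would sensibly resolve it by taking eligible women from 6.1 in every period and treating the 6.0 sentence as a limit on the offer.

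If the other reading were used throughout, the illustrated absolute effect would move from 15 points to between 12.75 and 17.6, depending on which population the planning rates describe. The test of no effect would keep its meaning. These figures rest on an assumed LARC share of 5 to 15%, equal in both periods and unaffected by the intervention, and the documents support no particular value. Confidence is high that the mismatch exists. Its practical size is unknown.
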